6.3.1 Description of Study Activities Performed by Abbott Field Representatives

Trained Abbott personnel may provide technical expertise and technical guidance on the use of the device. However, the Principal Investigator remains responsible for ensuring all clinical investigation data is collected as required per the CIP. An Abbott field representative may assist with obtaining procedure data from the EnSite system for documentation for the trial and/or downloading procedure data to a USB or external drive and sending to Abbott.

6.4 Pre-Discharge Visit (In-hospital)

Same day discharge after the ablation procedure is not allowed for the study, even if it is considered standard of care at some institutions. It is strongly recommended that the investigator performing the ablation procedure personally evaluates the subject on the evening of the procedure and/or the morning

following the procedure and maintains active surveillance of the subject's postoperative care and condition for at least 72-hours or prior to discharge, whichever occurs first.

The following are required testing for the Pre-Discharge Visit:

- Complete physical exam and 12-lead ECG
- Neurological assessment by a qualified physician and administration of the NIHSS by a certified assessor must be performed >12 hours post-procedure prior to discharge, but no later than 36 hours after the procedure.

NOTE: Subjects with new findings on the neurologic assessment/NIHSS are required to have a formal neurological consult and follow-up diffusion-weighted magnetic resonance imaging (MRI) of the brain. If contra-indicated for MRI, then an alternate form of imaging may be performed.

- Document AAD and anticoagulant drug usage
- Document adverse events and protocol deviations

If the subject requires an extended hospitalization due to a complication or other reason, the neurological exam and NIHSS assessment should be performed within 36-hours of the procedure. All other pre-discharge testing should be performed prior to discharge, but no later than 72 hours post-procedure.

6.5 Blanking and Therapy Consolidation Periods

A blanking period of 90-days will be employed after the initial ablation procedure, followed by a 90-day therapy consolidation period and then a 9-month evaluation period for a total of 15-months of follow-up. Early recurrence of AF, AFL, or AT within the blanking period or therapy consolidation period will not be considered treatment failures. During the blanking and therapy consolidation periods, adjustment of antiarrhythmic medications, cardioversions, and one repeat ablation procedure may be performed.

6.6 Follow-up Assessments

Subjects will undergo the following assessments described below at 7-days and at 3, 6, 12 and 15-months post-ablation.

7-Day (7 ± 2 days) Follow-up Visit

This visit constitutes a phone call to the subject after each ablation procedure (initial and if applicable, a repeat procedure) and requires documentation of the following:

- Document AAD and anticoagulant drug usage
- Document adverse events and protocol deviations
 - If the subject describes symptoms suggestive of pulmonary vein stenosis (e.g. shortness of breath, cough, and hemoptysis), have the subject schedule a visit with the investigator to determine if CT or MRI imaging of the pulmonary veins should be performed.
 - If the subject describes symptoms suggestive of atrioesophageal fistula such as chest pain, painful swallowing, fever, and/or describes symptoms of stroke, have the subject schedule a visit with the investigator immediately or go to the emergency room based on the severity of the symptoms.

- If the subject describes symptoms suggestive of cardiac tamponade (i.e., chest pain with hypotension) or if cardiac tamponade is suspected, the subject should be evaluated promptly by the investigator and a TTE performed.
- Document any cardiovascular healthcare utilization performed since the last scheduled study visit as defined in **Section 6.6.3**

3-Month (91 + 14 days) Follow-Up Visit

The 3-month follow-up visit is a scheduled in-person site visit.

- Provide the subject with a TTM device for monthly heart rhythm transmission and transmission of symptomatic episodes, if the subject does not have the device provided to them at the Baseline visit.
- When subjects are seen at the 3-month visit, it is recommended that they are weaned off AADs during the therapy consolidation period if they are doing well and have not discontinued these medications previous to this visit.
- 12-lead ECG
- Document AAD and anticoagulant usage
- Administer the AFEQT and EQ-5D-5L questionnaires
- Document any cardiovascular healthcare utilization performed since the last visit as defined in **Section 6.6.3**
- Document adverse events and protocol deviations
 - If the subject describes symptoms suggestive of pulmonary vein stenosis (e.g. shortness of breath, cough, and hemoptysis), complete CT or MRI imaging of pulmonary veins.
- Administer a 24-hour Holter monitor

6-Month (181 + 30 days) Follow-Up Visit

The 15-month follow-up visit is a scheduled in-person site visit.

- 12-lead ECG
- Document AAD and anticoagulant usage
- Administer the AFEQT and EQ-5D-5L questionnaires
- Document any cardiovascular healthcare utilization performed since the last visit as defined in **Section 6.6.3**
- Document adverse events and protocol deviations
 - If the subject describes symptoms suggestive of pulmonary vein stenosis (e.g. shortness of breath, cough, and hemoptysis), complete CT or MRI imaging of pulmonary veins.
- Administer a 24-hour Holter monitor

- Review TTM transmissions

6.6.1 Repeat Ablation Procedures

One ablation procedure is allowed during the blanking and therapy consolidation periods (within 180 days post-initial procedure) due to AF/AFL/AT recurrence without being considered an effectiveness endpoint failure. The repeat procedure must be performed with the TactiCath SE catheter using the recommended parameters listed in the *Instructions for Use* document and in **Section 6.3**. The TactiCath SE catheter should not be used for repeat procedures that occur ≥ 181 days after the initial procedure or if the subject requires a third ablation procedure at any time during the follow-up period.

Certain assessments need to be performed if a repeat ablation is required. Neurological assessment and administration of the NIHSS by a certified assessor must be performed within 14-days of the repeat ablation procedure. Thrombus assessment must be performed as outlined in **Section 6.2.6** prior to ablating the subject. Verification of the exclusion of pericardial effusion by ICE or TTE must also be performed prior to the conclusion of the procedure.

A 7-day (± 2 days) follow-up phone call to the subject will need to be conducted after the repeat procedure. All other follow-up visits will occur as previously scheduled from the initial ablation procedure. Note that the 90-day blanking period followed by a 90-day therapy consolidation period are still in place from the initial procedure.

If AF/AFL/AT recurrence (>30 second episode) occurs at any time after this second ablation procedure or after the therapy consolidation period (≥ 181 days post-initial procedure), the subject will be considered an effectiveness endpoint failure. If the subject requires a repeat procedure for AF/AFL/AT recurrence after the therapy consolidation period or the subject requires a third ablation procedure, then the subject will be considered an effectiveness endpoint failure regardless of documentation of a >30 second AF/AFL/AT episode.

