4.1.2 Primary Effectiveness Endpoint

The primary effectiveness endpoint for this clinical trial is freedom from AF/AFL/AT episodes of >30 seconds duration that is documented by an ECG (12-lead or TTM) or 24-hour Holter after the initial catheter ablation procedure through 15-months of follow-up (includes a 90-day blanking period followed by a 90-day therapy consolidation period). AF/AFL/AT recurrence during the blanking or therapy consolidation periods will not be considered a treatment failure. One repeat procedure is allowed for ablation of AF/AFL/AT recurrence during the blanking or therapy consolidation periods (≤ 180 days post-initial procedure) without being considered a treatment failure.

AF/AFL/AT recurrence will only be assessed by 12-lead ECG, TTM, and 24-hour Holter monitoring devices for assessment of this primary endpoint so that all subjects are monitored equally with devices of the same sensitivity and specificity. Collected ECG, TTM, and 24-hour Holter data from sites will be evaluated by a physician at a core laboratory for independent and unbiased assessment of AF recurrence for endpoint analysis.

There are multiple situations in which subjects will be considered primary effectiveness endpoint failures:

- If AF/AFL/AT recurrence (>30 second episode) occurs at any time after the therapy consolidation period (>180 days after the initial procedure), or
- If the subject requires a repeat procedure for the treatment of AF after the therapy consolidation period, the subject will be considered an effectiveness endpoint failure regardless of documentation of a >30 second AF/AFL/AT episode, or
- If the subject requires a second repeat procedure at any time after the initial procedure, or
- If the subject requires a new AAD or a previously failed AAD at a dose greater than the highest ineffective historical dose for AF after the therapy consolidation period, or
- If the subject requires a cardioversion (electrical or pharmacological) for the treatment of AF after the therapy consolidation period, or
- If the subject has a continuous atrial arrhythmia throughout a 12-lead ECG recording after the therapy consolidation period indicating arrhythmia recurrence, this will be considered sufficient documentation of recurrence unless there is evidence that the recorded arrhythmia is short-lived and less than 30 seconds.

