6.6.2 Unscheduled Visits

If a subject is seen by any physician for possible AF recurrence and/or arrhythmia associated symptoms outside of a regularly scheduled study visit and/or had an urgent care or emergency room visit regarding possible arrhythmia, these visits need to be documented as "Unscheduled Visits". Minimally, the following information should be documented for an unscheduled visit.

- 12-lead ECG, if performed during the visit
- Document AAD and anticoagulant usage
- Document adverse events and protocol deviations

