6.7 Core Laboratory

A core lab will be used for the collection, interpretation, and collation of data collected from the following sources:

- TTM
- 24-hour Holter monitoring
- 12-lead ECGs

The core lab will provide independent review of this data by appropriately trained personnel using standardized procedures to interpret TTM, 24-hour Holter, and 12-lead ECG tracings for adjudication of atrial arrhythmias. Findings will be communicated to the investigator and to Abbott. The core lab's adjudication findings will be used for analysis.

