	
2. The primary effectiveness endpoint for this clinical trial is freedom from AF/AFL/AT episodes of >30 seconds duration that is documented by an ECG (12-lead or TTM) or 24-hour Holter after the initial catheter ablation procedure through 15-months of follow-up (includes a 90-day blanking period followed by a 90-day therapy consolidation period). AF/AFL/AT recurrence during the blanking or therapy consolidation periods will not be considered a treatment failure. AF/AFL/AT recurrence will only be assessed by 12-lead ECG, TTM, and 24-hour Holter monitoring devices for assessment of this primary endpoint so that all subjects are monitored equally with devices of the same sensitivity and specificity. Collected ECG, TTM, and 24-hour Holter data from sites will be evaluated by a physician at a core laboratory for independent and unbiased assessment of AF recurrence for endpoint analysis.
 
There are multiple situations in which subjects will be considered primary effectiveness endpoint failures:
 
 • If AF/AFL/AT recurrence (>30 second episode) occurs at any time after the therapy consolidation period (>180 days after the initial procedure), or • If the subject requires a repeat procedure for the treatment of AF after the therapy consolidation period, the subject will be considered an effectiveness endpoint failure regardless of documentation of a >30 second AF/AFL/AT episode, or • If the subject requires a second repeat procedure at any time after the initial procedure, or • If the subject requires a new AAD or a previously failed AAD at a dose greater than the highest ineffective historical dose for AF after the therapy consolidation period, or • If the subject requires a cardioversion (electrical or pharmacological) for the treatment of AF after the therapy consolidation period, or • If the subject has a continuous atrial arrhythmia throughout a 12-lead ECG recording after the therapy consolidation period indicating arrhythmia recurrence, this will be considered sufficient documentation of recurrence unless there is evidence that the recorded arrhythmia is short-lived and less than 30 seconds.

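### Protocol 6.6.1 scores a recurrence between an allowed repeat ablation and day 180 as an effectiveness failure; the primary endpoint definition and the visible SAP do not

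*Protocol*

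**What the plan says.** The endpoint definition in Protocol 4.1.2 is explicit: "AF/AFL/AT recurrence during the blanking or therapy consolidation periods will not be considered a treatment failure". One repeat ablation by day 180 is permitted and is not itself a failure. Six failure criteria follow. Five apply only after the therapy consolidation period. The one that can be met earlier is the third: "If the subject requires a second repeat procedure at any time after the initial procedure".

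Appendix IV repeats the definition and the six criteria. Its first criterion counts a recurrence that "occurs at any time after the therapy consolidation period (>180 days after the initial procedure". SAP 1.4.2 carries the same definition and list. Protocol 6.5 states the rule again: "Early recurrence of AF, AFL, or AT within the blanking period or therapy consolidation period will not be considered treatment failures".

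Section 6.6.1, on repeat ablation, first agrees: "Note that the 90-day blanking period followed by a 90-day therapy consolidation period are still in place from the initial procedure". Its next paragraph then gives a failure rule that starts "If AF/AFL/AT recurrence (>30 second episode) occurs at any time after this second ablation procedure or after the therapy consolidation period". The therapy consolidation limb is dated to day 181 or later; the limb about the second ablation carries no date of its own. A third ablation is also a failure there, which matches the third criterion in 4.1.2.

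**The concern.** A scoring rule for the primary effectiveness endpoint should give one answer for each subject. As written, a subject who has the permitted repeat, has a documented recurrence before day 181 and does well afterwards can be scored either way, depending on which section is followed.

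This is a single-arm trial judged against a predetermined performance goal, so the success rate is itself the result. If both rules stay in the text, the choice between them could be made after outcomes are known. Review of tracings does not settle it. Protocol 6.7 has the core laboratory apply standardized procedures "to interpret TTM, 24-hour Holter, and 12-lead ECG tracings for adjudication of atrial arrhythmias"; that decides whether an arrhythmia is present, not whether one found before day 181 counts.

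**Working it through.** **1. The rules side by side**, for a recurrence of more than 30 seconds on or before day 180, after an allowed repeat:

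- Protocol 4.1.2: not a failure; no exception after a repeat.
- Protocol 6.5: not a failure; no exception after a repeat.
- Protocol Appendix IV: not a failure; no exception after a repeat.
- SAP 1.4.2: not a failure; no exception after a repeat.
- Protocol 6.6.1, timing note: both periods still run from the initial procedure.
- Protocol 6.6.1, failure rule, first limb: failure.

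The use of >180 days in one place and ≥ 181 days in another is not part of the conflict; in whole days they are the same.

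**2. Can the sentence be read so that the conflict disappears?** Only by applying the day-181 parenthesis to both limbs. Any recurrence after the second ablation would then count only if it also fell after consolidation, which the second limb already covers. The first limb would add nothing.

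**3. Does the failure list leave room for the 6.6.1 rule?** No. It has six criteria, five of them limited to the time after consolidation. The exception is a second repeat procedure. The definition therefore deals with early failure after a repeat, and recurrence after the first repeat is not listed.

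**4. Worked case.** Repeat on day 70; AF of more than 30 seconds on the 3-month Holter on day 98; no third ablation; no failure event after day 180. Day 98 is inside the visit window on either printing: 91 ± 14 gives days 77 to 105 (Table 4), and 91 + 14 gives days 91 to 105 (Section 6.6). Result: failure under 6.6.1, success under 4.1.2 and SAP 1.4.2.

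**5. Would such a recurrence be documented?** Yes, by several routes:

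- the 3-month ECG and Holter;
- TTM, monthly and with symptoms, from month 3;
- the 6-month Holter if done on days 151 to 180, which Table 4 allows (181 ± 30 days) and the Section 6.6 printing (181 + 30 days) does not;
- at unscheduled visits, a "12-lead ECG, if performed during the visit".

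Before month 3 no scheduled TTM is collected, so documentation depends mainly on unscheduled ECGs.

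**6. Direction.** The 6.6.1 rule adds failures to those in 4.1.2 and removes none. The number of successes falls or stays the same.

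**7. Size.** The documents give neither the share of subjects with a repeat by day 180 nor the share of those who recur before day 181. The population definitions (Protocol 8.1, SAP 2.1) and the effectiveness analysis (Protocol 8.2.1.2, SAP 2.3.1.2) are redacted. The following is illustration only and assumes a simple proportion.

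Shift = r × u, where r is the share with a repeat by day 180 and u is the share of those whose only failing event is a recurrence between the repeat and day 180.

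- Low, assumed: 0.05 × 0.05 = 0.0025, or 0.25 percentage points.
- High, assumed: 0.20 × 0.40 = 0.08, or 8 points.

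A second set of assumptions splits u into q (recurs in the window) and s (otherwise a success):

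- Low: 0.05 × 0.10 × 0.50 = 0.0025, or 0.25 points.
- High: 0.20 × 0.50 × 0.50 = 0.05, or 5 points.

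The range reflects the assumptions and nothing else. Nor is the effect of one subject fixed. On all 224 enrolled it would be 1/224 = 0.45 points. With the 20% attrition visible in the sample-size text, 224 × 0.80 = 179.2, and 1/179 = 0.56 points. Under a time-to-event estimator neither figure need apply.

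**The case against.** The visible text has a dominant rule. Four places, including the endpoint definition and SAP 1.4.2, agree that recurrence by day 180 does not count. The chronic-success secondary endpoint also counts recurrence only in the nine months after consolidation. An analyst working from SAP 1.4.2 alone would see no ambiguity. The outlier is one clause in a procedural section, straight after a note that both periods continue, and it may be loose drafting meant only to say that a repeat does not restart the blanking period. In addition, Protocol 8.2.1.2 and SAP 2.3.1.2 are redacted and may state the rule.

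Much of this stands. Loose drafting is plausible, and a clarifying rule in the redacted text cannot be excluded. But no visible passage sets an order of precedence, and 6.6.1 is the section specific to repeat ablation, so a reader could equally take it as the special rule. Redacted text cannot remove a conflict between two visible sections of the protocol.

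A reader might go further and infer that the SAP itself holds two rules, that power is compromised, or that the trial's result would turn on this clause. The documents support none of these. The visible SAP states one rule. The effectiveness goal, expected rate and sample-size reasoning for this endpoint are redacted. The upper ends of the illustrative ranges are assumptions, not estimates.

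**Conclusion.** Wrong as written. Protocol 6.6.1 makes a recurrence between an allowed repeat ablation and day 180 an effectiveness failure; Protocol 4.1.2, 6.5, Appendix IV and SAP 1.4.2 say it is not, and 6.6.1 conflicts with its own note on timing. Confidence is high for the textual conflict. Whether scoring is unresolved in practice cannot be known, because the operative analysis text is redacted in both documents.

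The direction is certain for the count of successes: the 6.6.1 rule lowers it or leaves it alone. The size cannot be computed and may be small. The single-procedure secondary endpoint is untouched, since any repeat fails there under either rule. The point should be fixed because it concerns the primary endpoint and costs almost nothing to correct, not because of any estimated effect.

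**What to change.** Before analysis, reconcile the passages to one scoring rule.

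- **Consistent with the visible endpoint definitions:** in the 6.6.1 failure sentence, delete the limb about recurrence after the second ablation, leaving recurrence after the therapy consolidation period, and keep the third-ablation criterion. Cost: one clause.
- **If the stricter rule was intended:** state it identically in Protocol 4.1.2, 6.5, Appendix IV and SAP 1.4.2. Then check it against the chronic-success secondary endpoint (Protocol 4.2 and Appendix IV; SAP 1.4.3.2 and 2.3.2.2). Otherwise a subject off antiarrhythmic drugs could fail the primary endpoint on an early recurrence and still count as a chronic success. Cost: one sentence in four places, plus that check.

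In either case, confirm that the redacted text of Protocol 8.2.1.2 and SAP 2.3.1.2 carries the same rule. A sensitivity analysis under the other reading is optional. No extra patients, visits or data are needed.

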6.6.2 Unscheduled Visits

If a subject is seen by any physician for possible AF recurrence and/or arrhythmia associated symptoms outside of a regularly scheduled study visit and/or had an urgent care or emergency room visit regarding possible arrhythmia, these visits need to be documented as "Unscheduled Visits". Minimally, the following information should be documented for an unscheduled visit.

- 12-lead ECG, if performed during the visit
- Document AAD and anticoagulant usage
- Document adverse events and protocol deviations

6.6.3 Healthcare Utilization Documentation

Healthcare utilization for cardiac-related hospitalizations (inpatient or outpatient), emergency room visits, and/or urgent care visits in the year previous to enrollment (consent) in this trial will be documented. Additionally, subjects will be interviewed at each scheduled visit to determine if they had any cardiac-related hospitalizations (inpatient or outpatient), emergency room visits, and/or urgent care visits since their last scheduled visit. Source documentation for these visits should be obtained and a Healthcare Utilization form completed.

6.6.4 Patient Reported Outcome Measures – AFEQT and EQ-5D-5L Questionnaires

The coordinator or designee will administer patient-reported outcome questionnaires. It is important the subject understands the meaning of all words and instructions in the questionnaires. The subject should be instructed to ask any questions about the questionnaires if further explanation is needed. Once the questionnaires are completed, the coordinator or designee will review for completeness to verify that all questions have been answered according to the directions provided.

The following patient-reported outcome measures will be collected:

- AF Effect on Quality of Life Survey (AFEQT)
- EuroQol Five Dimensions Questionnaire (EQ-5D-5L)

The AFEQT questionnaire is an AF-specific health-related quality of life questionnaire designed to be used in different clinical settings including clinical research, survey studies, or clinical practice to assess the impact of AF on a patient's quality of life and possibly to assess changes with treatment. The AFEQT is a self-administered questionnaire that should take approximately 5-minutes to complete and consists of 20 questions. Four of the 20 questions target AF-related symptoms, 8 questions evaluate daily function, and 6 questions assess AF treatment concerns on a 7-point Likert scale (1= "Not at all..." to 7 "Extremely..."). Two of the questions are not scored and are to assess the subject's satisfaction with treatment. The AFEQT questionnaire should ideally be administered prior to the subject being seen by the physician to ensure the subject's responses are not influenced by the physician's evaluation. If other questionnaires are to be administered at the same time, the AFEQT should be completed first so that answers to other questionnaires do not influence the response to the AFEQT.

The EQ-5D-5L questionnaire is a standardized measure of health status that is applicable to a wide range of health conditions and treatments. It provides a simple descriptive profile and a single index value for health status that can be used in the clinical and economic evaluation of health as well as in population health surveys. EQ-5D-5L is designed for self-completion and is ideally suited for use in postal surveys, in clinics, and in face-to-face interviews and takes only a few minutes to complete. The questionnaire includes five dimensions assessing mobility, self-care, usual activities, pain/discomfort, and anxiety/depression. Each dimension is measured based on responses to 5 levels: no problems, slight problems, moderate problems, severe problems, and extreme problems. Respondents evaluate their overall health status using a visual analogue scale, which can easily be converted to quality-adjusted life years for cost utility analysis.

Note that it will not be a deviation for the 6-month and 12-month visits administered by phone to not have the visual analogue scale of the EQ-5D-5L questionnaire completed. Research personnel should use the EQ-5D-5L Script for Telephone Interview questionnaire for visits conducted over the phone.

